# 1 SYNOPSIS

Title: Phase 2, Multicenter, Double-blind (Sponsor-unblinded), Randomized, Placebo-Controlled Study of the Safety and Efficacy of Elagolix in Women with Polycystic Ovary Syndrome		
Background and Rationale:	Polycystic ovary syndrome (PCOS) is a complex and heterogeneous endocrine and metabolic disorder characterized by chronic oligoanovulation, androgen excess, and polycystic ovaries. Despite being one of the most common hormonal disorders in women of reproductive age, few therapeutic options are available for women with PCOS. Elagolix has the potential to impact the disordered pituitary and ovarian hormonal dynamics in women with PCOS.	
Objective and Endpoints:	Objective The objective of the study is to assess the pharmacokinetics, pharmacodynamics, safety, and efficacy of elagolix in women with PCOS.  Endpoints Primary Endpoint  The proportion of menstrual cycle responders  Key Secondary Endpoint  Change from Baseline to Week 1 in the area under the luteinizing hormone (LH) serum concentration-time curve (AUC).  Additional Efficacy Endpoints  Proportion of complete menstrual cycle responders  Change from Baseline in the LH serum AUC at each scheduled assessment during the Treatment Period  Change from Baseline in the follicle-stimulating hormone (FSH) serum AUC at each scheduled assessment during the Treatment Period  Change from Baseline in total and free testosterone serum concentration at each scheduled assessment during the Treatment Period  Number of menstrual bleeding episodes during the Treatment Period  Number of ovulations based on weekly serum progesterone levels during the Treatment Period  Proportion of subjects with at least 2 ovulations during the Treatment Period  Endpoints related to hyperandrogenism — Patient Global Impression (PGI) for both acne and hirsuitism; change from Baseline at each scheduled assessment during the Treatment Period for the following: acne measured with total lesion count and investigator's global assessment (IGA), hirsutism	

	
 
Endpoints related to metabolic features - change from Baseline at each scheduled assessment during the Treatment Period for the following: glycated hemoglobin (HbA1c), fasting insulin/glucose, body mass index (BMI), lipids, waist circumference
 
Change from Baseline at each scheduled assessment during the Treatment Period for additional hormones: androstenedione, anti-Mullerian hormone (AMH), estradiol (E2), progesterone
 
Change from Baseline in ovarian volume at each scheduled assessment during the Treatment Period
 
Endpoints related to the subject's quality of life: change from Baseline in domains from the Polycystic Ovary Syndrome Questionnaire (PCOSQ) (emotions, body hair, weight, infertility problems, and menstrual problems), and the Menstrual Bleeding Questionnaire (MBQ) at each scheduled assessment during the Treatment Period.
 
	
Investigators:	Multicenter	
Study Sites:	Approximately 54 sites (United States, including Puerto Rico).	
Study Population and Number of Subjects to be Enrolled:	Approximately 130 women 18 to 35 years of age with PCOS and a BMI 18.5 to 38 kg/m², inclusive	
Investigational Plan:	This is a Phase 2, multicenter, randomized, double-blind (sponsor-unblinded), 6-month, placebo-controlled, parallel group study of elagolix in women with PCOS. Eligible subjects will be randomized 2:2:2:2:2:3 (active treatment to placebo) to 25 mg twice daily (BID), 50 mg once daily (QD), 75 mg BID, 150 mg QD, 300 mg QD, or placebo (20 subjects in each active treatment group and 30 subjects in the placebo group).	
Key Eligibility Criteria:	Women 18 to 35 years of age with PCOS and a BMI 18.5 to 38 kg/m², inclusive	
Study Drug and Duration of Treatment:	Elagolix or matching placebo will be administered during the Treatment Period.  The duration of the study could be up to 42 weeks, which includes an 8-week Washout (if necessary), a 6-week Screening Period, a 24-week Treatment Period, and a 30-day Post-Treatment Follow-up Period.	
Date of Protocol Synopsis:	02 October 2020	

## 2 INTRODUCTION

## 2.1 Background and Rationale

#### Why Is This Study Being Conducted

Polycystic ovary syndrome (PCOS) is a complex and heterogeneous endocrine and metabolic disorder characterized by chronic oligo-anovulation, androgen excess, and polycystic ovaries. Despite being one of the most common hormonal disorders in women of reproductive age, few therapeutic options are available for women with PCOS.

Elagolix sodium (hereinafter "elagolix,") is an oral, short-acting, nonpeptide, gonadotropin-releasing hormone (GnRH) antagonist that competitively inhibits the GnRH receptors in the pituitary gland. Elagolix, unlike injectable GnRH analogs, produces a dose-dependent suppression of pituitary and ovarian hormone levels in women, i.e., from partial ovarian suppression at lower doses to nearly full suppression at higher doses. A detailed discussion of the preclinical toxicology, metabolism, pharmacology, and pharmacokinetics (PK) of elagolix in humans and a summary of clinical studies can be found in the Investigator's Brochure.

Elagolix has the potential to improve the disordered pituitary and ovarian hormonal dynamics in women with PCOS.

#### **Clinical Hypothesis**

Elagolix will lower luteinizing hormone (LH) secretion while maintaining follicle-stimulating hormone (FSH) secretion and consequently:

- 1. Lower serum testosterone concentrations
- 2. Restore normal menstrual cycles in women with PCOS
- 3. Improve ovulation
- 4. Improve hyperandrogenic symptoms

# 2.2 Benefits and Risks to Subjects

Women with PCOS have symptoms of oligomenorrhea, hirsutism, and anovulation due to excess LH secretion. Elagolix has the potential to improve this symptom complex by reducing LH secretion and potentially restoring a normal LH/FSH ratio. Preliminary data show that at low doses of elagolix, LH is preferentially inhibited compared with FSH. As of 20 August 2018, 4569 subjects have been exposed to elagolix; the safety profile of elagolix is well established even at doses higher than those planned for administration in this study. Thus, the benefit/risk profile for the study is favorable.

For further details, please see findings from completed studies, including safety data in the elagolix Investigator's Brochure.

Considering the coronavirus disease-2019 (COVID-19) pandemic, the benefit and risk to subjects participating in this study has been re-evaluated. Based on the limited information to date, no additional risk to study participants is anticipated with the use of elagolix.

### 3 STUDY OBJECTIVES AND ENDPOINTS

## 3.1 Objectives

The objective of the study is to assess the PK, pharmacodynamics (PD), safety, and efficacy of elagolix in women with PCOS.

## 3.2 Primary Endpoint

The primary endpoint is the proportion of menstrual cycle responders.

## 3.3 Key Secondary Endpoint

Change from Baseline to Week 1 in the area under the LH serum concentration-time curve (AUC).

## 3.4 Additional Endpoints

- 1. Proportion of complete menstrual cycle responders
- 2. Change from Baseline in the LH serum AUC at each scheduled assessment during the Treatment Period
- 3. Change from Baseline in the FSH serum AUC at each scheduled assessment during the Treatment Period
- 4. Change from Baseline in total and free testosterone serum concentration at each scheduled assessment during the Treatment Period
- 5. Number of menstrual bleeding episodes during the Treatment Period
- 6. Number of ovulations based on weekly serum progesterone level during the Treatment Period
- 7. Proportion of subjects with at least 2 ovulations during the Treatment Period
- 8. Endpoints related to hyperandrogenism Patient Global Impression (PGI) for both acne and hirsutism; change from Baseline at each scheduled assessment during the Treatment Period for the following: acne measured with total lesion count and investigator's global assessment (IGA), hirsutism measured with Ferriman–Gallwey (FG) score
- 9. Endpoints related to metabolic features change from Baseline at each scheduled assessment during the Treatment Period for the following: glycated hemoglobin (HbA1c), fasting insulin/glucose, body mass index (BMI), lipids, waist circumference
- 10. Change from Baseline at each scheduled assessment during the Treatment Period for additional hormones: androstenedione, anti-Mullerian hormone (AMH), estradiol (E2), progesterone

- 11. Change from Baseline in ovarian volume at each scheduled assessment during the Treatment Period
- 12. Endpoints related to the subject's quality of life: change from Baseline in domains from the Polycystic Ovary Syndrome Questionnaire (PCOSQ) (emotions, body hair, weight, infertility problems, and menstrual problems) and the Menstrual Bleeding Questionnaire (MBQ) at each scheduled assessment during the Treatment Period.

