#### **Demographic and Laboratory Assessments**

- 5. Adult female, 18 to 35 years of age, inclusive, at the time of Screening.
- 6. Body mass index (BMI) 18.5 to 38 kg/m², inclusive at the time of Screening
- 7. A diagnosis of PCOS with subject meeting each of the following historical criteria:
  - Clinical hyperandrogenism or biochemical hyperandrogenism based on physical examination or laboratory findings; and
  - History of ovarian dysfunction indicated by menstrual irregularity: oligomenorrhea (menstrual interval > 35 days or ≤ 8 menstrual cycles per year) or amenorrhea (no menses in 6 consecutive months or greater); and
  - Cycle length > 35 days in the 3 months prior to Baseline based on subject self-report.
- 8. Laboratory values must meet the following criteria within the Screening Period prior to the first dose of study drug:
  - Must not have FSH level > 10 IU/L
  - Elevated testosterone (total testosterone or free testosterone calculated by central laboratory)
  - Aspartate aminotransferase (AST) and alanine aminotransferase (ALT) < 3 times the upper limit of the reference range and bilirubin < 2 times the upper limit of the reference range (unless known diagnosis of Gilbert's disease).
  - Negative urine and/or serum pregnancy test(s) during the Washout (if necessary) and/or Screening Periods, and a negative urine pregnancy test immediately before administration of the first dose of study drug.
  - Subjects must have neither hepatitis B nor C based on the presence of the following:
    - Hepatitis B surface antigen (HBsAg)
    - Hepatitis C virus antibody (HCV Ab) and detectable HCV RNA
    - Equivocal viral test results should be repeated.

- No clinically significant abnormalities in clinical chemistry, hematology, or urinalysis (excluding findings associated with the disease under study).
- Screening labs may be retested once prior to Baseline; for further retesting, contact the TA MD.
- An adequate endometrial biopsy that shows no clinically significant endometrial pathology during Screening (or within 12 months prior to Screening if documentation provided) or endometrial thickness < 5 mm on Screening TVU.

- Must have a normal Papanicolaou (Pap) smear result as described in, Operations Manual (Appendix F), Pap Test Eligibility (applies to subjects ≥ 21 years of age at Screening or age at which Pap smears are routinely performed according to local guidelines).

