# SCREENING:

0	
U	

□ INTERVIEW	
 
Subject informed consent
 
Eligibility criteria
 
Medical history (including alcohol, nicotine, and drug use)
 
Gynecological/obstetrical history
 
AE assessment
 
	
 
Prior/concomitant therapy
 
Contraceptive         counseling/dispense         nonhormonal contraceptives as         necessary
 

■ PRO	
 
Dispense electronic diary (e-Diary) and begin daily e-Diary
 
	
 
Columbia Suicide Severity Rating Scale (C-SSRS) Screening
 

** EXAM	
 
12-lead electrocardiogram (ECG)
 
Height, weight, and waist circumference
 
Vital signs
 
Papanicolaou (Pap) test (if needed)
 
Urine pregnancy test
 
Physical examination
 
Gynecological (pelvic and breast) examination
 
	
 
Magnetic resonance imaging (MRI) if required
 
Pelvic ultrasound (transvaginal ultrasound [TVU] and transabdominal ultrasound [TAU])
 
Endometrial biopsy (if required)
 
Dual energy X-ray absorptiometry (DXA) scan
 

-	op - III I	man

- ▲ CENTRAL LAB
- Clinical laboratory tests (chemistry, hematology, lipid panel, urinalysis)
- Liver transaminases (alanine aminotransferase [ALT], aspartate aminotransferase [AST]) and fractionated bilirubin
- Screening endocrine hormones/test:
  - Follicle-stimulating hormone (FSH)
  - Dehydroepiandrosterone sulfate (DHEAS)
  - Reflexive thyroid-stimulating hormone (TSH)
  - Prolactin
  - 17-OH-progesterone (17-OH-P)
  - Fasting insulin
  - Glycated hemoglobin (HbA1c)

- Endocrine hormones:
  - Testosterone/sex hormone binding globulin (SHBG)
  - Estradiol (E2)
  - Progesterone
- Serology (hepatitis B and C) screens

NOTES:

Pap test will be performed in subjects ≥ 21 years of age during the Screening Period only if the subject has not had a Pap test or colposcopy within 6 months of the Screening visit and documentation is present to confirm eligibility as outlined in Figure 1 Pap Test Eligibility. Endometrial biopsy will be performed only if it has not been performed within 12 months of the Screening visit and documentation is

present to confirm eligibility. Results of the endocrine hormones/test must be received and reviewed by site for eligibility prior to Baseline.

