8.0 Efficacy Analyses

8.1 General Considerations

All efficacy analyses will be conducted using the FAS. Unless otherwise specified, each elagolix dose group will be compared to placebo. All statistical tests will be conducted at an alpha level of 0.1 (two-sided). A test will be deemed significant if the P value rounded to three decimal places is less than or equal to 0.1 unless otherwise specified.

Unless otherwise specified, categorical data will be summarized by frequencies and percentages for each treatment group and overall; continuous data will be summarized by the mean, standard deviation, median, minimum, and maximum for each treatment group and overall. For the analyses of change from baseline, the within-group changes will be summarized with the mean, standard deviation, and the median; between-group differences will be summarized with the mean, standard error, P value, and the 90% CIs.

Baseline refers to the last non-missing value obtained prior to or on Study Day 1.

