8.5.2 LH, FSH, testosterone and other hormones

The changes from baseline to each scheduled assessment of the hormone parameters will be analyzed using a mixed-effects model with repeated measures (MMRM). If appropriate, the natural logarithmic transformation or other transformation may be employed for the hormone parameters. The MMRM analysis will include the fixed categorical effects of treatment, visit, treatment-by-visit interaction, baseline FG score ($< 8, \geq 8$), and baseline normal/obese status ($\text{BMI} < 30, \geq 30$), subject as a random effect, and the continuous fixed covariate of baseline hormone value.

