8.5.5 Change from baseline for other clinical efficacy endpoints

Change from baseline to each scheduled assessment for the following endpoints will be analyzed: acne measured with total lesion count and investigator global assessment of acne, hirsutism measured with Ferriman–Gallwey (FG) score, metabolic features (Hb A1c, fasting insulin/glucose, body mass index (BMI), lipids [LDL cholesterol, HDL cholesterol, total cholesterol, triglycerides], waist circumference), ovarian volume, and endpoints related to subject's quality of life (PCOSQ [emotions, body hair, weight, infertility problems, and menstrual problems], and MBQ). The analysis will be based on

one-way ANCOVA with treatment group as the main effect, and baseline FG score (< 8 , ≥ 8), baseline normal/obese status ($\text{BMI} < 30$, ≥ 30), and baseline value of the corresponding endpoint being analyzed as the covariates.

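### For testosterone, E2 and the metabolic endpoints, the SAP leaves out an untreated Screening value that could narrow the treatment comparisons at almost no cost

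*Protocol*

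**What the plan says.** Protocol 3.4 lists among the additional endpoints "Change from Baseline in total and free testosterone serum concentration at each scheduled assessment during the Treatment Period". It also lists change from Baseline in E2, fasting insulin and glucose, HbA1c, lipids, BMI and waist circumference.

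Operations Manual 2.1 schedules testosterone with SHBG, E2, "Fasting insulin", HbA1c, chemistry, the lipid panel, weight and waist at Screening. Operations Manual 2.2 schedules the same items again at Baseline. Glucose is part of the chemistry panel (Operations Manual Table 1). Any washout comes before Screening (Protocol 4.1), and the first dose is taken the morning after the Baseline visit (Operations Manual 3.18). Both values are therefore untreated.

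SAP 8.1 keeps one of them: "Baseline refers to the last non-missing value obtained prior to or on Study Day 1". The repeated-measures model for hormones in SAP 8.5.2 has FG and BMI strata, "subject as a random effect, and the continuous fixed covariate of baseline hormone value". The ANCOVA in SAP 8.5.5 has the same two strata and the "baseline value of the corresponding endpoint being analyzed as the covariates". Neither model uses the Screening value when a Baseline value exists.

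For testosterone, the Screening value is also an entry condition. Protocol 5.1, criterion 8, requires "Elevated testosterone (total testosterone or free testosterone calculated by central laboratory").

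**The concern.** One laboratory value is an imperfect measure of a woman's usual level. Adjusting for a single value leaves some of the stable difference between women in the residual, and a second untreated value would remove part of it. That value is already scheduled. It should also be nearly complete, because testosterone, glucose and HbA1c are checked for eligibility and screening results must be reviewed before Baseline.

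At stake is precision in a dose-ranging study with about 20 women per dose. Lower serum testosterone is the first consequence named in the clinical hypothesis (Protocol 2.1), and testosterone suppression is part of the dose rationale (Protocol 4.2).

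**Working it through.** **The plan's own figure.** The only stated power is at least 85% for the primary endpoint: 10% against 50% responders, 30 against 20 women, two-sided 0.05, Pearson chi-square (SAP 2.4). Pooled proportion = (3 + 10)/50 = 0.26. Null SE = √(0.26 × 0.74 × (1/30 + 1/20)) = 0.1266; alternative SE = √(0.09/30 + 0.25/20) = 0.1245. Power = Φ((0.40 − 1.96 × 0.1266)/0.1245) = 88.9%, so the statement holds. No power, SD or correlation is given for the endpoints discussed here, and this point does not affect that figure.

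**Inputs.** Arms of 20 and 30 (SAP 2.4); two-sided alpha 0.10 for efficacy tests (SAP 8.1). All correlations are assumptions.

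**Case 1: equal correlation r between any two occasions, no selection.** Residual variance is 1 − r² with one pre-dose value and 1 − 2r²/(1 + r) with two. The ratio is (1 + 2r)/(1 + r)².

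| r | one value | two values | ratio | 20 women act like |
|---|---|---|---|---|
| 0.3 | 0.910 | 0.862 | 0.947 | 21.1 |
| 0.5 | 0.750 | 0.667 | 0.889 | 22.5 |
| 0.7 | 0.510 | 0.424 | 0.830 | 24.1 |
| 0.8 | 0.360 | 0.289 | 0.802 | 24.9 |

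Variance falls by 5% to 20%, and intervals narrow by 3% to 10% (square root of the ratio).

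**Case 2: testosterone, selected on Screening.** Suppose only women above some percentile of the Screening value enter, and let k be the variance of the Screening value after that cut, relative to before. Selecting on a covariate leaves the two-covariate residual variance unchanged. With Baseline alone it becomes V − C²/V, where V = r²k + 1 − r² and C = r²k + r − r². For r = 0.7 with the top half kept, k = 1 − 2/π = 0.363, V = 0.688, C = 0.388, giving 0.469. The ratio is 0.424/0.469 = 0.90, against 0.83 without selection. For r = 0.5 to 0.8 and cuts at the 30th to 70th percentile, the ratio runs from 0.961 to 0.848, a fall of about 4% to 15%.

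**Case 3: correlation decays with time.** Let r be the Baseline–outcome correlation, c Screening–Baseline and s Screening–outcome. The proportional fall is (s − rc)²/((1 − c²)(1 − r²)).

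- r = 0.6, c = 0.6, s = 0.5: 0.0196/0.4096 = 4.8%.
- r = 0.7, c = 0.7, s = 0.6: 0.0121/0.2601 = 4.7%.
- r = 0.7, c = 0.8, s = 0.6: 0.0016/0.1836 = 0.9%.
- Pure first-order decay (s = rc): 0%.

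**In terms of power.** Take a comparison that now has 80% power at two-sided 0.10. Its new power is Φ((1.645 + 0.842)/√ratio − 1.645).

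- Case 1: 82% (r = 0.3), 84% (r = 0.5), 87% (r = 0.8).
- Case 2: 81% to 85%.
- Case 3: 80% to 82%.

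**Cost.** With 130 women at one visit, ANCOVA leaves 130 − 1 − 5 − 2 − 1 = 121 residual degrees of freedom. A second covariate leaves 120, so even a useless one costs less than about 1% of precision.

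**The case against.** The strongest reply is that nothing here is wrong. Adjusting for the last pre-dose value is unbiased under randomisation and already removes most of what any pre-dose value can remove. Only additional endpoints are affected, in a proof-of-concept study whose SAP (section 10) makes no claim to Type I error control. All of that stands.

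The reply also holds on size. A reader might take the 11% to 20% reduction for r = 0.5 to 0.8 as the expected gain. The documents do not support this: it needs equal correlations and no selection. Screening may precede Baseline by up to six weeks, extendable, and outcomes run to Week 24, so some decay is plausible. Selection is not confined to testosterone either. Criterion 15 caps Screening glucose, HbA1c and total testosterone, and criterion 6 limits BMI. No passage ties E2 sampling to a cycle phase, so a low r is plausible there; the same applies to progesterone, which is also drawn at both visits. The models already carry FG and BMI strata, which the formulas above ignore and which may hold part of the information for BMI and waist.

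The reply does not remove the point. The value is already scheduled, entering it leaves the randomised comparison unbiased, and the worst outcome is about one lost degree of freedom. The practical gaps (a missing Baseline-visit value, a log scale) can be closed with stated rules. Non-fasting samples, which the Operations Manual allows, make the covariate noisier but do not bias it.

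**Conclusion.** The point holds as a missed efficiency gain. A reader might infer that the testosterone and metabolic analyses are biased or invalid, or that the trial's main conclusion is weakened. Neither follows: the models are valid, the primary endpoint does not use these values, and the key secondary endpoint (LH AUC) has serial sampling at only one pre-dose visit.

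The plausible range is a 0% to 20% fall in residual variance: about 5% to 20% under equal correlations of 0.3 to 0.8, about 4% to 15% for testosterone under the selection and correlations assumed above, and about 0% to 5% with decay. Every figure rests on correlations that the documents do not give, and the testosterone figure also on an assumed severity of selection. The gain may be slight for E2. This is worth doing because it is nearly free, not because the present plan is deficient.

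**What to change.** In SAP 8.5.2 and 8.5.5, for each endpoint measured at both visits:

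- Keep change from Baseline as the response, and keep the SAP 8.1 definition of Baseline.
- Add the last Screening-visit value (the retest, if there was one) as a second continuous covariate, on the same scale as the Baseline covariate, for example both on the log scale.
- State a rule for women whose Baseline-visit value is missing, so that Screening already serves as Baseline and no woman is dropped. Entering the same value in both terms is one such rule.
- Do not average the two values into the change score. Women are selected on high Screening testosterone, so an averaged baseline would exaggerate within-group falls and change the endpoint. As a separate pre-randomisation covariate, the Screening value does neither.

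Write this in before database lock with a dated rationale. The sponsor is unblinded throughout (Protocol 7.1), so a covariate added after results are seen would carry little weight.

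The cost is a short addition to two SAP sections and about one degree of freedom. No new samples, visits or women are needed.
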